#### ***Data collection and management***

All data will be stored in a secure REDCap database. Surveys will be collected online using secure electronic data capture in REDcap. The final trial dataset will only be available to select members of the research team (LA, LM, TI). The final dataset will not be made publicly available to protect the confidentiality of participants, but de-identified data could be made available upon request. Baseline surveys will collect detailed data on socioeconomic variables, including age, sex, gender identity, income, and food security, medical history, and the secondary outcomes described above (nutrition, physical activity, sedentary time, mental health). Follow-up surveys administered every 2 months (at 2, 4 and 6 months) will collect updated data on secondary outcomes. Participants in both the control and intervention groups will receive a \$30 gift card at the time of each survey completion. We will continue to collect data from participants if they deviate from protocol unless there is withdrawal from the study. To ensure confidentiality, a unique study id number will be used for the weight and activity data and linked at McMaster by the research team to the main study database.

#### ***Safety protocols and unanticipated outcomes***

Possible adverse outcomes may include concerns related to mental health, including eating disorders, or frustration due to weight gain/no change. Expectations of the research will be laid out before enrollment and feelings such as these can be addressed as part of the motivational interviewing process. Our research team including the research assistants/interviewers and physician co-investigator (EA) are equipped to assess the situation and provide necessary referrals. Medical and counselling services are available on campus for all

students. If participants raise any concerns of self-harm or harm to others, then safety protocols will be followed.

### ***Data Analysis***

The analysis and reporting of our results will be done according to the CONSORT guidelines.(51) The data analyst will be blinded. Patient screening, randomization, allocation, and follow-up numbers will be illustrated in a flow diagram. Baseline data will be reported in a table for both groups (Intervention and Control) and summarised as means (standard deviation) or median (first quartile, third quartile) for continuous variables and counts (percent) for categorical variables. Data on feasibility outcomes will be measured and compared to pre-determined thresholds for interpretation. The primary analysis will be by intention-to-treat (data from participants will be analyzed according to their allocation irrespective of whether they received that intervention). For these purposes, a complete data set is required. Multiple imputation techniques will be used to manage missing data points. Comparison of groups for secondary outcomes will be reported descriptively for this pilot study. No formal significance testing for comparisons of the secondary clinical outcomes will be made because this is a pilot study with *a priori* sample size determined based on feasibility outcomes only. It is well established that there are sex and gender differences in obesity.(52) Disaggregated data on sex and gender will be reported.

### ***Sample size***

Our sample size estimation was based on feasibility considerations and calculated using WINPEPI.(53) Using a 95% confidence level, assuming that 80% of the participants will complete the study with a 7.5% margin of error, 110 participants are needed (55 intervention and 55 control). This sample size is not sufficiently powered to make between-group comparisons but will provide accurate data on feasibility and estimates of effect size variability that will inform the sample size calculation of a larger definitive trial.

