### ***Measurement of Outcomes***

Table 1 describes all outcomes. The primary feasibility outcomes that will be measured are recruitment, retention, data completion, and participant satisfaction. We will consider a larger trial feasible if recruitment rates are  $\geq 50\%$ , retention rates are  $\geq 80\%$ , and the data completion rate for all secondary clinical outcomes is  $\geq 80\%$ . Participant satisfaction with different aspects of the study will be measured at the exit questionnaire using a Likert scale and semi-structured qualitative free-text responses.

Secondary outcomes will include BMI change from baseline to 6-months. Interventions are more successful if longer than 4 months in duration.(36) All study participants will have one in-person visit with the research assistant at the start of the study where baseline weight and height will be measured using standardized methods with calibrated study instruments. Participants (both intervention and control) will then receive a Fitbit activity tracker to wear for the duration of the study. Study participants will be asked to visit the

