**Table 1. Summary of all outcome measures and method of analysis**

Outcome measure	Variable Type	Measurement	Method of analysis
Primary Feasibility Outcomes			
Recruitment rate	Binary	% of eligible participants who are recruited from all those who contact the research team to learn about the study	Feasibility threshold of ≥50%

Retention rate	Binary	% of participants who complete 6-month follow-up	Feasibility threshold of $\geq 80\%$ .
Data completion	Binary	% of secondary outcomes with no missing data	Feasibility threshold of $\geq 80\%$ .
Satisfaction	Continuous	Mean score on a 7-point Likert scale	Mean satisfaction score $\geq 4$
Secondary Outcomes			
BMI change	Continuous	Change in BMI from baseline to 6-month follow-up, weight measures using wifi enabled smart scales	Mean, SD
Physical activity	Binary	International Physical Activity Questionnaire (IPAQ)	Mean, SD
	Continuous	Minutes per day from activity trackers	Mean, SD
Sedentary time	Binary	International Sedentary Assessment Tool (ISAT)	Mean, SD
Nutrition	Continuous	National Cancer Institute's Dietary Screener Questionnaire (DSQ)	Mean, SD
Mental health	Binary	Depressive symptoms (CESD-10) score $>10$ , Anxiety (GAD-7) score $>10$ ,	N, %
Health-related quality of life	Continuous	Quality of Life (EQ-5D-5L)	Median, IQR

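### Data completion, a primary feasibility outcome with an 80% threshold, is stated in three ways that can give opposite results for the same trial at the planned 80% retention

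*Combined protocol and SAP*

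**What the plan says.** The Sample size section rests on a single proportion. "Using a 95% confidence level", it reads: "assuming that 80% of the participants will complete the study with a 7.5% margin of error, 110 participants are needed", split as 55 per arm.

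Retention is defined in Table 1 as the percentage "of participants who complete 6-month follow-up", with a threshold of at least 80%.

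Data completion also has an 80% threshold, but its definition changes from place to place:

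- **Abstract:** the share of weights measured and of surveys completed.
- **Measurement of Outcomes:** one of three conditions for calling a larger trial feasible, alongside recruitment of at least 50% and retention of at least 80%: "and the data completion rate for all secondary clinical outcomes is" to be at least 80%.
- **Table 1:** the percentage "of secondary outcomes with no missing data".

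None of the three states whether the denominator is everyone randomised or those still in the study, or whether visits are pooled. The secondary outcomes include BMI change from baseline to 6 months.

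The progression rule also has two forms. Measurement of Outcomes joins its conditions with an and. Reporting and interpretation uses green, yellow and red, asks for a minimum of one green outcome, and gives no cut-offs for yellow or red.

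**The concern.** Feasibility is the primary objective, so the result of this pilot is whether each threshold was met. If one threshold can be read in several ways, the team can report it as met or missed from the same data, and can choose the reading after seeing them.

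One reading also overlaps with retention. A participant with no 6-month assessment has no 6-month BMI change. If completion is judged on that outcome over all randomised, every loss to follow-up counts against both criteria, and a completer without a weight counts against completion as well. Completion then repeats the retention criterion in a stricter form, and the stated 80% retention is no longer the rate that the rule demands. Because the planning value sits exactly on the threshold, there is no slack for this.

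**Working it through.** **Inputs from the documents.** Confidence level 95% (z = 1.96); assumed completion 0.80; margin 0.075; N = 110 (Sample size). Thresholds of 80% for retention and data completion (Measurement of Outcomes, Table 1). Surveys at baseline and months 2, 4 and 6, so 4 per participant (Data collection and management). Weights at baseline and then monthly (Measurement of Outcomes), taken here as 7; that count is an inference, since the schedule in Figure 2 is not fully legible.

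**Input not in the documents.** c, the share of completers with a usable 6-month value. Range shown: 90% to 100%.

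**1. The plan's own figure.** n = z²p(1−p)/d² = 1.96² × 0.80 × 0.20 / 0.075² = 109.3, rounded up to 110. It reproduces. The half-width at 110 is 7.48 percentage points.

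**2. Retention mark.** At least 80% of 110 means at least 88. Exact binomial P(X ≥ 88 | n = 110):

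| True retention | Probability of meeting the mark |
|---|---|
| 75% | 0.134 |
| 80% | 0.557 |
| 85% | 0.941 |

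**3. Data completion pooled over visits (one reading of the Abstract).** With 88 completers fully observed and 22 dropouts who supply baseline only:

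- Surveys: (88 × 4 + 22 × 1) / (110 × 4) = 374/440 = 85.0%.
- Weights: (88 × 7 + 22 × 1) / (110 × 7) = 638/770 = 82.9%.

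Dropouts who stay longer raise these, up to 95% for surveys (3 of 4 supplied) and 97.1% for weights (6 of 7). If baseline is not counted and dropouts supply nothing after it, both fall to 80.0%.

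**4. Data completion per outcome at 6 months over all randomised (one reading of Measurement of Outcomes).** Expected completion of 6-month BMI change = 0.80 × c:

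| c (assumed) | Expected completion | P(at least 88 of 110) | Retention needed for 80% expected (0.80/c) |
|---|---|---|---|
| 100% | 80.0% | 0.557 | 80.0% |
| 98% | 78.4% | 0.393 | 81.6% |
| 95% | 76.0% | 0.193 | 84.2% |
| 90% | 72.0% | 0.036 | 88.9% |

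**5. Table 1 taken literally.** The unit is the outcome, and an outcome counts only if nothing is missing. With 0.20 × 110 = 22 participants lost, no outcome that needs a 6-month value qualifies, so the score for those outcomes is 0%.

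**6. The same trial under the three readings.** Take 80% retention, c = 95% at every visit, and dropouts who supply half of their scheduled assessments on average (an assumption). Pooled: 0.80 × 0.95 + 0.20 × 0.50 = 86%. Per outcome at 6 months: 76%. Literal Table 1: 0%. The first meets the threshold and the other two do not.

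**The case against.** A reader might infer something stronger: that the plan's own assumption contradicts its threshold, so the feasibility rule is expected to fail. The documents do not support that.

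- **Failure needs an added assumption.** With 80% retention and fully observed completers, expected 6-month completion is exactly 80%, which meets the threshold, and the chance of meeting it equals that for retention, 0.557. The lower probabilities depend on c, which the documents do not give. There is some reason to expect c below 100%: later visits may be virtual while the scale is in the study office, and the plan treats adherence to these weigh-ins as an open question. That makes c < 1 plausible but does not fix its size.
- **The effect depends on the definition.** Pooling over visits can cover month 6 and keep all randomised in the denominator, and still exceed 80%. Retention can then be the binding mark.
- **The cap is not strict.** Table 1 does not say which measures make up completion of 6-month follow-up. If a weight is required, every completer has one. If the survey alone defines it, someone could have a weight without counting as retained.
- **A missed mark need not stop progression.** Under the traffic-light rule one green outcome is the stated minimum, and yellow allows a modified larger trial.
- **Table 1 is terse.** The 0% result is unlikely to be what the authors intend, since the other two sections speak of rates.

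All five points stand. They remove the claim of expected failure but not the ambiguity: the outcome of a primary feasibility criterion turns on a choice that the plan leaves open. Each threshold is to be reported separately, so a wrong or selected reading would appear in the results even if it did not block a larger trial.

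**Conclusion.** The concern holds as a problem of definition and of what the thresholds deliver, not as an arithmetic error. The 110 is a correct precision calculation. At the planned 80% retention, data completion can be at least 82.9% for weights and 85% for surveys (pooled, baseline counted, completers fully observed, 7 weights assumed), about 72% to 80% (6-month BMI change over all randomised, c from 90% to 100%), or 0% (Table 1 literally, for outcomes needing a 6-month value). On the middle reading the chance of meeting the threshold runs from 0.557 down to 0.036, and the criterion largely duplicates retention. Separately, because the planning value equals the retention threshold, that mark is met with probability of only about 0.56 if true retention is 80%; the plan does not say so. This should be corrected before results are interpreted.

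**What to change.** 1. **One definition of data completion**, used identically in the Abstract, Measurement of Outcomes and Table 1: the percentage of scheduled weights and surveys obtained at each follow-up, among participants still in the study at that visit. It then measures something that retention does not.
2. **Report beside it** the percentage of all randomised participants with a 6-month BMI change. The conditional rate is easier to meet, so this figure must be shown with it.
3. **Reconcile the two progression rules.** Say whether the joint conditions in Measurement of Outcomes or the traffic-light rule in Reporting and interpretation governs, and give the green, yellow and red cut-offs.
4. **In Sample size**, keep the 80% planning value and N = 110, and add the chance of meeting the retention threshold at true rates of 75%, 80% and 85%: 0.13, 0.56 and 0.94.

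Replacing the planning value with a higher retention rate is not a sound remedy. At the same 7.5% margin it would lower the calculated N; at 84.2%, for example, 1.96² × 0.842 × 0.158 / 0.075² is about 90.9, so 91.

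The cost is wording only, with no added participants or visits.

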### ***Reporting and interpretation***

Study results will be reported following the CONSORT extension for randomized pilot and feasibility trials guideline(54) For each feasibility outcome, we will report whether the feasibility threshold was met and use a traffic light system to inform progression to a larger trial. Green: proceed to larger trial; yellow: proceed with some modifications; red: larger trial not feasible. At least one feasibility outcome must be green. Any deviations to the protocol will be recorded and reported in the final manuscript. Study results will be shared with participants through a final report and published in a peer-reviewed manuscript.

## **CONCLUSIONS**

Although it is well recognized that the causes of obesity are complex, many obesity trials have evaluated a narrowly defined “one size fits all” intervention. We will evaluate the feasibility of a tailored intervention delivered through motivational interviewing sessions with a trained research assistant interviewer. This approach will allow participants to set their own behavioural change goals. Further, we are evaluating the feasibility of a targeted or risk stratification approach to an obesity intervention to determine if higher-risk young adults benefit more from the intervention.

This intervention is designed to be flexible to focus on a broad range of health behaviours so study participants can set behavioural change goals related to the behaviours that they think are most important to them. While for some participants, this may focus on traditional, obesity-related risk factors such as diet or physical activity, for other participants this may include behaviours related to sleep, mental health, substance use, or time management. All these behaviours have the potential to either directly or indirectly impact obesity prevention.

Our feasibility trial will inform future larger RCTs for obesity prevention. The results of this study have the potential to directly contribute to the primary prevention of several types of cancer by testing an intervention that could be scalable to public health, post-secondary education, or primary care settings. This study is pragmatic with the option of remote visits for MI. Unlike traditional MI, this format with a trained

interviewer is feasible and the results of the risk stratification objective may inform who would benefit the most from a larger-scale program. This pilot study will provide proof of concept for an intervention that could be expanded to other settings such as public health, post-secondary education, or primary care. If successful, this program could be implemented in university wellness services and may have a profound impact on the primary prevention of an established and highly prevalent chronic disease risk factor.

### **List of Abbreviations**

BMI	Body Mass Index
CESD-10	Centre for Epidemiologic Studies Depression Measure-10
DSQ	Dietary Screener Questionnaire
EQ-5D-5L	Euroqol -5D
GAD-7	Generalized Anxiety Disorder -7
HiREB	Hamilton Integrated Research Ethics Board
IPAQ	International Physical Activity Questionnaire
ISAT	International Sedentary Assessment Tool
MI	Motivational Interviewing
RCT	Randomized Controlled Trial

### **DECLARATIONS**

**Ethics approval and consent to participate:** Study participants will provide written consent and this study has been approved by the Hamilton Integrated Research Ethics Board (HiREB Project Number: 14675).

**Consent for publication:** Not applicable.

[figure not shown]
**Availability of data and materials:** Not applicable.

**Competing interests:** The authors declare that they have no competing interests.

**Funding:** This research is funded by a Proof of Concept Intervention Grant in Primary Prevention of Cancer (Action Grant) of the Canadian Cancer Society and the Canadian Institutes of Health Research-Institute for Cancer Research (CCS grant #707228/CIHR-ICR grant # POC-181032).

**Authors' contributions:** All authors contributed to the development of the study design and contributed to writing the manuscript. All authors read and approved the final manuscript.

Figure 1. Overview of the Study Design

**Figure 2. SPIRIT schedule of enrolment, interventions, and assessments.**

Control Group:								
Educational materials								
ASSESSMENTS:								
Height Measurement			X					
Weight measurement			X	X	X	X	X	X
Study questionnaires			X		X			X

**Table 1. Summary of all outcome measures and method of analysis**

Outcome measure	Variable Type	Measurement	Method of analysis
Primary Feasibility Outcomes			
Recruitment rate	Binary	% of eligible participants who are recruited from all those who contact the research team to learn about the study	Feasibility threshold of ≥50%

Retention rate	Binary	% of participants who complete 6-month follow-up	Feasibility threshold of $\geq 80\%$ .
Data completion	Binary	% of secondary outcomes with no missing data	Feasibility threshold of $\geq 80\%$ .
Satisfaction	Continuous	Mean score on a 7-point Likert scale	Mean satisfaction score $\geq 4$
Secondary Outcomes			
BMI change	Continuous	Change in BMI from baseline to 6-month follow-up, weight measures using wifi enabled smart scales	Mean, SD
Physical activity	Binary	International Physical Activity Questionnaire (IPAQ)	Mean, SD
	Continuous	Minutes per day from activity trackers	Mean, SD
Sedentary time	Binary	International Sedentary Assessment Tool (ISAT)	Mean, SD
Nutrition	Continuous	National Cancer Institute's Dietary Screener Questionnaire (DSQ)	Mean, SD
Mental health	Binary	Depressive symptoms (CESD-10) score $>10$ , Anxiety (GAD-7) score $>10$ ,	N, %
Health-related quality of life	Continuous	Quality of Life (EQ-5D-5L)	Median, IQR

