**The primary study objective is:**

1) To determine the feasibility (enrollment, retention, data completion, satisfaction) of a 6-month behavioural and educational intervention to promote healthy behaviours for obesity prevention among young adults.

The **secondary objectives are:**

2) To determine the effects of the 6-month behavioural and educational intervention, compared to an educational intervention only, on change in BMI, health behaviours (nutrition, physical activity and sedentary time), health-related quality of life, and mental health (depression and anxiety).

3) To explore whether obesity risk stratification tools identify young adults who may be more successful in an obesity intervention.

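### The enrolment criterion is only a conversion percentage, so it can be met whatever number is enrolled and however long that takes

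*Combined protocol and SAP*

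**What the plan says.** The primary objective is "To determine the feasibility (enrollment, retention, data completion, satisfaction"), so enrolment comes first among the four things the pilot has to establish.

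Two places set the test. Under Measurement of Outcomes the plan begins "We will consider a larger trial feasible if recruitment rates are" at least 50%, alongside conditions on retention and data completion. Table 1 defines the recruitment rate as the percentage "of eligible participants who are recruited from all those who contact the research team to learn about the study" and gives the rule as "Feasibility threshold of ≥50" per cent. Neither place gives a number to be enrolled or a period in which to enrol them. The Abstract gives thresholds for retention and data completion but none for enrolment.

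The target number is stated only under Sample size: "110 participants are needed (55 intervention and 55 control"). It is derived from the precision of the completion proportion and is not tied to the recruitment criterion. Study Design and Population lists the recruitment channels without a duration or an expected number of contacts. Reporting and interpretation adds a traffic-light scheme with no numerical cut-offs between colours, and requires a minimum of one green outcome.

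**The concern.** A conversion percentage does not change with scale or with calendar time. If half of those who come forward join, the criterion is met, whether 20 or 220 people came forward and whether they did so over one term or several years. The measure is called a rate, but it has no time unit.

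The pilot exists to inform a decision about a larger trial. For enrolment, that decision needs to know whether the planned number could be found and at what pace, as well as how many interested students agree to join. As written, the criterion could report enrolment as feasible in a pilot that stopped well short of 110. The shortfall would also erode the precision on retention for which the sample size was chosen, and no rule in the plan would respond to it. Because the traffic-light scheme asks for a minimum of one green outcome, enrolment could be the outcome that supplies it.

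**Working it through.** **Inputs from the plan.** Target 110; "Using a 95% confidence level"; "assuming that 80% of the participants will complete the study"; "with a 7.5% margin of error" (all Sample size). Recruitment threshold 50% (Measurement of Outcomes; Table 1).

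**Inputs assumed.** All numbers of contacts, eligible people and recruits below, and all recruitment durations. The documents give none of these.

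**Step 1: reproduce the planned sample size.** For a single proportion, n = z² p(1−p) / d². With z = 1.96, p = 0.80 and d = 0.075, n = 3.8416 × 0.16 / 0.005625 = 109.27, rounded up to 110. The plan's figure is reproduced. The half-width at n = 110 is 1.96 × √(0.16/110) = 0.0748, or 7.5 points.

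**Step 2: apply the 50% rule to different totals.** The half-width in the last column is 1.96 × √(0.16/n), with n the number recruited.

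| Recruited / eligible contacts (assumed) | Conversion | Threshold met? | Share of 110 | 95% half-width at 80% retention |
|---|---|---|---|---|
| 10 / 20 | 50.0% | yes | 9% | 24.8 points |
| 30 / 60 | 50.0% | yes | 27% | 14.3 points |
| 60 / 110 | 54.5% | yes | 55% | 10.1 points |
| 110 / 200 | 55.0% | yes | 100% | 7.5 points |

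In the third row the 110 contacts are an assumed count that happens to equal the target. The share of target is therefore the same fraction as the conversion. All four rows meet the criterion, and only the last reaches the planned number.

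**Step 3: vary the time.** Take 110 recruited from 200. Over 4 months that is 110/4 = 27.5 per month; over 24 months it is 110/24 = 4.6 per month. Conversion is 55% in both cases. At an unchanged pace, a larger trial of any size would need 24/4 = 6 times as long to recruit in the second case, and the criterion cannot tell the two apart.

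**Step 4: check the denominator.** The Table 1 wording refers both to eligible participants and to everyone who makes contact. Suppose 300 contacts, 200 of them eligible and 110 recruited. On eligible contacts the result is 110/200 = 55%, which meets the threshold. On all contacts it is 110/300 = 36.7%, which does not, although the full target was enrolled. Insensitivity to number and time holds under either reading, but whether the criterion is met can depend on which reading is used.

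**The case against.** Uptake among interested students is a legitimate feasibility quantity and a useful planning input, and the plan gives it a definition and a threshold. That stands. A reader might infer that the criterion tells us nothing about recruiting a larger trial, or that the primary objective goes unanswered for enrolment. The documents do not support that: enrolment is answered for uptake and left open for number and pace.

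A reader might also infer that a failed recruitment will be scored green. The plan reports whether each threshold was met and uses a traffic light, but it never says that meeting 50% equals green. That link is implied only.

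Nor would a shortfall be hidden. Data Analysis commits to a flow diagram with screening and randomization numbers, and Reporting and interpretation commits to the CONSORT pilot extension and to reporting deviations. Sixty randomised against a stated 110 would be plain to see. What remains is that no prespecified rule acts on it, and nothing in the text commits to reporting recruitment time.

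The Sample size section says the pilot will inform the later sample size calculation; it makes no promise about trial duration. If dates are recorded, pace could be calculated at reporting, so the gap is one of prespecification.

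Finally, Figure 1 is not shown and Figure 2 is cut, so a recruitment period may be given there. That would not alter the criterion, which is worded in full under Measurement of Outcomes and in Table 1.

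**Conclusion.** The point holds in this limited form. The enrolment criterion measures conversion among people who contact the team, and it can be met at any total and over any duration. Taken alone it shows uptake, but not whether 110 was reached or how quickly. In the assumed example of 60 from 110, it is met at 55% of target with the retention margin at 10.1 points instead of 7.5.

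The algebra, that a ratio ignores scale and time, needs no assumption. The sizes do: every count and duration used here is illustrative. They are not evidence that slow or short recruitment is likely at this university, nor a forecast for a larger trial, which the Conclusions section envisages extending to other settings. The sample size of 110 is not in dispute. The change should be made because the present rule could report enrolment as feasible when recruitment had failed. It does not threaten the validity of the rest of the pilot.

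**What to change.** Under Measurement of Outcomes and in the recruitment row of Table 1, replace the single percentage with a two-part criterion:

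- (a) 110 participants randomised within a recruitment period of a stated number of months, with randomisations per month reported. The sponsor must supply the period, since none appears in the text available.
- (b) Conversion of at least 50%, with the denominator stated as eligible people who contact the team, and the percentage of all contacts reported alongside.

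State that the enrolment threshold counts as met, and is green under the traffic-light scheme, only if both parts hold, and that meeting one part alone is not green.

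The cost is a sentence in the text, one table row, and dated records of contact and randomisation. There is no added burden on participants. Short or slow recruitment could now miss a criterion that it would previously have met. Because this changes a primary feasibility criterion in a registered trial with ethics approval, an ethics amendment and a registry update may be needed.
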